## *Physical Assessment*

The purpose of a physical assessment of physical functioning of the elderly prior entering an exercise program is to identify the individuals at risk and effectiveness of the program design.

1. The participant will have their heart rate and blood pressure measured to determine if they are at risk of high blood pressure, of which was one of the leading cause of death and disability in 2010 usually due to unhealthy diet habits, higher percentage of body fat, and physical inactivity (Whelton, P.K. et al, 2018). This can further be supported by the measurements from the Bioelectrical Impedance Analysis (BIA) scale (Kabiri et al, 2015) to determine the individuals body composition.
2. As mentioned previously, risk of falling is closely associated with physical disability and chronic pain. Hence the participant will be assessed on mobility, lower body muscle strength, and balance ability to determine the effectiveness of the intervention:
  - a. Timed Up and Go (TUG) (Podsiadlo and Richardson 1991): a chair with handle is placed 3m away from an obstacle. The individual is instructed to rise from the chair without touching the handles, walk to the point then return to the chair in a seated position as quickly as possible. The rating is based on the number of seconds it takes for the individual to return to initial position where: less than 10 sec. is normal, less than 20 sec. is independent and can displace without aid, and lastly, less than 30 sec. demonstrates that that individual has difficulty walking and requires assistance with daily activity.
  - b. 4-Stage Balance Test “modified” (Phelan et al, 2015): requires the individual to stand in 4 different positions progressively for 10 sec. each. The 4 positions include: stand with feet side-by-side, place the instep of one foot next to the other foot’s big toe, tandem stand, and stand with one foot. If the tandem stand cannot be held for 10 sec. indicates that the elderly is at risk of falling.
  - c. 30 seconds sit to stand test (Rikli, R.E. & Jones, C.J., 2001): the

individual is instructed to sit in the middle of the chair (17 inches from the ground) with hand across the chest and both feet flat on the ground. With back straight, the individual is to rise from the chair to a standing position then return to sitting position for 30 seconds. The score is compared with the norm to evaluate on the risk of fall. This test is chosen over other sit to stand tests because of its ability to differentiate the lower strength ability among wider range of older adults with a intraclass correlation coefficient and valid measurement for lower body strength is 0.89 and 0.77 respectively (Rikli, R.E. & Jones, C.J., 1999).

3. Physical functioning is also assessed to determine their capability in performing daily activities involving the upper body:
  - a. Grip strength (Lino et al, 2016) is commonly used as a biomarker for elderly's health status (Bohannon, 2019): The individual is asked to sit with their back straight arms straight on the side. The dynamometer set at the second handle will be squeezed as hard as possible alternating hands after trial. 2 trials will be taken on each hand and the sum of it will be calculated.
4. Aerobic is assessed using the 2-Minute Step Test (Johnston et al, 1999) : The individual is instructed to lift their knee to the height halfway between iliac crest to patella for a total of 2 minutes. The score is the number achieved with the right knee throughout 2 minutes at the given height.

## **Data Analysis**

Data will be analysed using a pre-post analysis based on different time points. For the main outcome measures of depressive symptoms/risks, wellbeing, and personal recovery, mixed ANOVA will be used to assess changes from T0/Intake to T1/exit between the two groups. To test for sustained effect after completion of intervention, mixed ANOVA will be used to assess depressive symptoms/risks, wellbeing, pain acceptance, physical ability, and symptoms of pain from T1/Exit to T2/FU within- and between- subjects. All results will be reported with the appropriate effect sizes, along with statistical significance and confidence intervals.

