## **OBJECTIVES**

The objective is to establish evidence of Acceptance and Commitment Therapy (ACT) in combination with exercise in:

Primary Outcomes

- 1) Reducing pain intensity and interference;
- 2) Reducing depression;

Secondary Outcomes

- 3) Reducing anxiety;
- 4) Increasing psychological flexibility;
- 5) Increasing pain-related self-efficacy;
- 6) Increasing quality of life;
- 7) Increasing physical functioning

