## **METHODS**

### Design

This study adopts a cluster randomized trial design comparing older adults with chronic pain receiving ACT and exercise intervention to two arms: 1) art and exercise; and 2) treatment as usual (control group). 15-20 elderly from 10 different mental health service centres will be randomized to the experimental, sham, or active control group.

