### Participants

The effect size from previous literature and pilot data (0.25), an alpha=0.05, and power=0.8 was used to derive the total sample size of 135 participants. Assuming 10% attrition, total sample size = 150. Older adults with chronic pain (n=150) recruited from collaborating NGOs will be randomized into 3 different arms: 1) ACT and exercise; 2) art and exercise; and 3) treatment as usual.

Inclusion criteria are:

- age 60 years or above; and
- have depressive symptoms of mild level or above (PHQ > 5)
- have chronic pain (>3 months)
- able to give informed consent to participate

Exclusion Criteria:

- known history of autism, intellectual disability, schizophrenia-spectrum disorder, bipolar disorder, Parkinson's disease, or dementia
- (temporary exclusion criteria) imminent suicidal risk difficulty in communication
- have had stroke, fracture, cardiovascular disease, cardiovascular surgery, artery disease, surgery on vertebrae, and knee replacement in the past 6 months
- physical activity prohibited by a medical professional

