### Assessment Procedures

After basic screening, assessments will be conducted by trained social services staff and trained research assistants employed by the University of Hong Kong for the intervention group.

Assessments will be conducted for all 3 arms at baseline (T0/Intake), completion of intervention (2 months, depending on individual condition) or drop-out (T1/Exit), and follow-up at 3 months (T2/FU) from discharge. Assessment will last for around 60 minutes for all participants.

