### *Primary Outcomes*

1. Feeling and Function in existence of pain: Brief Pain Inventory (BPI) (Cleeland, 1994) aims to evaluate the individual's pain experience and its effect on physical function on daily activities. The tool consists of 11 items, using an 11-point rating, of which 0 indicates not interference and 10 as interferes completely. The Cronbach's alpha coefficients for interference and severity subscales were .88 and 0.80 respectively (Cleeland, 1991). A validation on the Taiwanese population of BPI (BPI-T) was done by Ger et al in 1999.
2. Depression: The Patient Health Questionnaire (PHQ-9) (Kroenke, Spitzer, & Williams, 2001): a 9-item instrument that incorporates depression diagnostic criteria with other leading major depressive symptoms, and rates the frequency of the symptoms which factors into the scoring severity index. PHQ-9 scores of 5-9,

10-14, 15-19, 20 and above represent mild, moderate, moderately severe, and severe depression. The Cronbach's alpha coefficients for Primary Care Study and Ob-Gyn Study were .89 and 0.86 respectively. A validation on the Chinese version of PHQ- 9 was done by Yeung, Y. in 2010.

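### The intake-to-exit analysis leaves out pain, a primary outcome, names main outcomes with no stated measure, and compares two groups in a three-arm trial

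*Protocol*

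**What the plan says.** The protocol's Objectives list two primary aims, the first being "Reducing pain intensity and interference" and the second the reduction of depression. The Primary Outcomes section attaches an instrument to each: the "Brief Pain Inventory (BPI") for pain and the PHQ-9 for depression.

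The design has three arms. The Design section describes older adults "receiving ACT and exercise intervention to two arms: 1) art and exercise; and 2) treatment as usual (control group"). The Participants section says they "will be randomized into 3 different arms: 1) ACT and exercise; 2) art and exercise; and 3) treatment as usual". Under Assessment Procedures, "Assessments will be conducted for all 3 arms at baseline (T0/Intake), completion of intervention", and again at follow-up three months after discharge.

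The Data Analysis section specifies two analyses:

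- **T0 to T1:** "For the main outcome measures of depressive symptoms/risks, wellbeing, and personal recovery, mixed ANOVA will be used to assess changes from T0/Intake to T1/exit", with the comparison made "between the two groups".
- **T1 to T2:** a mixed ANOVA for sustained effect, within and between subjects. It covers depressive symptoms and wellbeing, and also "pain acceptance, physical ability, and symptoms of pain from T1/Exit to T2/FU".

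**The concern.** The Data Analysis section appears to have been written for a different set of outcomes and a different number of arms from those in the rest of the protocol. Three things follow.

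- **Pain.** Treatment is given between T0 and T1, and pain is the first primary aim, yet the T0-to-T1 list omits it. The analysis that does name pain is meant to show that an effect lasts, but no specified analysis first establishes that effect from baseline.
- **Main outcomes.** The list adds two constructs that the protocol does not define as primary. One of them cannot be measured with any instrument described.
- **Comparison.** With three arms, two unnamed groups could mean different questions. ACT and exercise against art and exercise asks what ACT adds to a programme that shares the exercise. ACT and exercise against treatment as usual asks what the whole package does.

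Left like this, the main outcome and the comparator could be chosen after the data are seen, and a claim about pain in either direction would have no pre-specified baseline-to-exit test behind it.

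**Working it through.** No figure in the protocol is disputed. The check sets its sections side by side and then works through what the specified pain analysis can show.

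**1. Primary outcomes against the T0-to-T1 list**

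| Stated primary outcome | Instrument | In T0-to-T1 analysis? | In T1-to-T2 analysis? |
|---|---|---|---|
| Pain intensity and interference | BPI | No | Yes, as symptoms of pain |
| Depression | PHQ-9 | Yes | Yes |

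A T0-to-T1 test is specified for 1 of 2 primary domains. The opening sentence of Data Analysis promises a pre-post analysis in general terms. It names no outcome, and the next sentence gives a T0-to-T1 list without pain.

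**2. Named main outcomes against the measures**

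| Main outcome in Data Analysis | Stated objective? | Instrument in the protocol |
|---|---|---|
| Depressive symptoms/risks | Yes, primary | PHQ-9 |
| Wellbeing | Not under that name | None linked; the SF-12 is labelled quality of life and is secondary |
| Personal recovery | No | None |

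So 1 of 3 matches a primary outcome, 1 is unmapped and 1 is unmeasured. Pain acceptance, in the T1-to-T2 sentence, is also linked to no scale. The CompACT-SF is collected, but as a measure of psychological flexibility.

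**3. Groups**

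Design, Participants and Assessment Procedures all give 3 arms. Data Analysis gives 2 groups and does not identify them. Three arms allow 3 pairs, and the Design section names 2 of these as the comparisons of interest.

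**4. What the T1-to-T2 pain analysis can show**

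Let the comparator's pain fall by *c* by T1 and the ACT arm's by *c + D*, both fully held at T2. Let *b* be any difference in mean pain at baseline (ACT minus comparator). The ACT-minus-comparator difference is then:

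- at T0: *b*
- at T1: *b − D*
- at T2: *b − D*

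The contrasts are:

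- Group by time, T0 to T1: (*b − D*) − *b* = −*D*. This is the treatment effect, free of *b*.
- Group by time, T1 to T2: (*b − D*) − (*b − D*) = 0. This test rejects only at its 0.05 level, whatever the size of *D*.
- Between subjects, averaged over T1 and T2: [(*b − D*) + (*b − D*)]/2 = *b − D*. This contains the effect, but mixed with any baseline difference.

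If the benefit were instead wholly lost by T2, the T1-to-T2 group-by-time contrast would be *b* − (*b − D*) = +*D*. A significant result would then signal loss of benefit.

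**The case against.** The strongest reply is that pain is not left without any between-arm test. The T1-to-T2 analysis has a between-subjects term, and in a randomised trial a comparison of post-treatment levels is a legitimate, if less efficient, test of treatment. This stands: with *b* = 0 the term equals −*D*, so a maintained pain effect could be detected. What it does not supply is a test of change from baseline. The zero contrast above applies to the interaction only. The baseline also matters more here than usual: the Design section calls the trial cluster randomised with 10 centres. If centres are the unit, that is about 10/3 ≈ 3.3 per arm, too few to rely on *b* being close to zero.

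Second, wellbeing and pain acceptance may have been meant as the SF-12 and CompACT-SF, and such mapping is often left to the statistical analysis plan. That is plausible, and this part is the least serious. But the protocol makes quality of life secondary, so calling wellbeing a main outcome still conflicts with it. No such reading is available for personal recovery.

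Third, the two groups may be loose wording for the two comparators. It may be, but the sentence does not say so, and its plain reading is a single comparison of two groups.

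Fourth, the correction has consequences. Three scores (BPI severity, BPI interference, PHQ-9) across two comparisons make 3 × 2 = 6 tests. If these were independent, the chance of at least one false positive would be 1 − 0.95⁶ ≈ 0.26. Also, if the effect size of 0.25 is Cohen's f, a simple two-group comparison with 135/3 = 45 per arm has about 65% power, ignoring clustering and any gain from the baseline measure. Both are fair cautions about how the tests are organised and how large the trial is. Neither is a reason to leave the primary outcome out of the main analysis.

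Finally, the statistical analysis plan is not at hand. It could fill a gap, but here the protocol states a rule that contradicts its own objectives and design. A plan that followed it would omit the pain test, and a plan that departed from it would conflict with the protocol.

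**Conclusion.** The concern holds, and the section must be corrected. The contradiction reaches the first-listed primary outcome, the list of main outcomes and the main comparison. The specified pain analysis spans the 3-month follow-up and does not measure change over the roughly 2-month intervention. The conclusion rests on the wording of the protocol alone. The zero interaction additionally assumes full maintenance of the benefit from T1 to T2.

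**What to change.** Reword the Data Analysis section of the protocol:

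- State that the main outcomes are BPI pain severity, BPI pain interference and PHQ-9, each analysed from T0 to T1.
- Replace the reference to two groups with the two comparisons of the Design section: ACT and exercise against art and exercise, and ACT and exercise against treatment as usual.
- Delete personal recovery.
- Delete wellbeing and pain acceptance, or map each to a collected scale (for example SF-12 and CompACT-SF) at its stated secondary level.
- Keep the T1-to-T2 analysis of pain as a test of maintenance, alongside the T0-to-T1 test.
- State the order of the primary tests or the adjustment for them, here or in the statistical analysis plan. This is optional in the protocol.

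The cost is a few sentences. The BPI and PHQ-9 are the listed primary measures, and assessments at T0 and T1 are already scheduled in all three arms, so these analyses need no new data collection. Whether 150 participants give enough power for each pairwise comparison is a separate question that the rewording does not settle.

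### The trial is declared cluster randomised, but the planned mixed ANOVA has no centre term and the text leaves open whether centres or people are randomised

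*Protocol*

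**What the plan says.** Design in the protocol opens with "This study adopts a cluster randomized trial design". Its next sentence makes people the object of allocation: "15-20 elderly from 10 different mental health service centres will be randomized to the experimental, sham, or active control group". Participants does the same: "Older adults with chronic pain (n=150) recruited from collaborating NGOs will be randomized into 3 different arms". No sentence says that centres are allocated to arms.

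For the first period, Data Analysis states that "mixed ANOVA will be used to assess changes from T0/Intake to T1/exit between the two groups". For the second it again uses mixed ANOVA, described as "from T1/Exit to T2/FU within- and between- subjects". Neither sentence mentions centre, a random effect above the participant, or a cluster-robust error. The sample size paragraph mentions no ICC or design effect.

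**The concern.** In a trial that randomises centres, part of any difference between arms is difference between the 3 or 4 centres that make up each arm. A mixed ANOVA with participants as its error unit counts that part as treatment effect, so its p-values and confidence intervals are too optimistic for every outcome whose change is correlated within centres.

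Analysing change from T0 to T1 does not cure this. It removes stable differences between centres, but not changes that people in one centre share. Shared change is plausible here because staff employed by the NGOs co-facilitate both active programmes.

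If individuals are randomised within centres, this mechanism disappears, but then the declared design is wrong. The correct analysis cannot be chosen until the unit is stated.

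**Working it through.** **Inputs from the protocol.** Design: 10 centres, 15 to 20 people each, three arms. Participants: effect size 0.25, alpha 0.05, power 0.8, 135 participants, 10% attrition, 150 in total. Data Analysis: mixed ANOVA from T0 to T1 and from T1 to T2.

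**Assumptions.** ICC of the change score 0.01, 0.02, 0.05 or 0.10; equal centre sizes; centres split 3/3/4; 0.25 read as Cohen's f (the protocol does not name the metric).

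**1. The plan's own sample size.** 135 / 0.9 = 150, so the attrition step reproduces. The 135 does not follow from the stated inputs alone. With f = 0.25, a one-way ANOVA needs 159 for three groups and 128 for two. A repeated-measures between-groups test with three groups and two time points gives 135 if the correlation is 0.7, a value the protocol does not state. Every variant tried that comes near 135 treats participants as independent, so no allowance for clustering is visible.

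**2. What the named test does.** With two time points, the time-by-group test is a one-way F test on change scores. Its error df are 135 − 3 = 132 to 150 − 3 = 147. With centres as the unit, they are 10 − 3 = 7. The variance of an arm mean is multiplied by 1 + (m − 1) × ICC. For m = 15 this is 1.14, 1.28, 1.70 and 2.40 at the four ICC values; for m = 20 it is 1.19, 1.38, 1.95 and 2.90.

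**3. Type I error of the nominal 5% test that ignores centre.** Simulation with no treatment effect, 40,000 runs per cell, equal ICC in all arms:

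| Comparison | m per centre | ICC 0 | 0.01 | 0.02 | 0.05 | 0.10 |
|---|---|---|---|---|---|---|
| 3 vs 3 centres | 13 | 4.8% | 6.3% | 7.6% | 12.0% | 19.1% |
| 3 vs 3 centres | 15 | 5.0% | 6.7% | 8.4% | 13.1% | 21.0% |
| 3 vs 3 centres | 20 | 5.0% | 7.2% | 9.7% | 16.4% | 25.3% |
| 3/3/4 centres | 13 | 4.8% | 6.9% | 8.8% | 15.6% | 26.2% |
| 3/3/4 centres | 15 | 5.1% | 7.1% | 9.6% | 16.9% | 29.4% |
| 3/3/4 centres | 20 | 5.2% | 8.1% | 11.9% | 21.9% | 36.2% |

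An F test on centre means gives 4.7 to 5.3% in the same cells. A separate simulation (10,000 runs, split 4/3/3, m = 15) gives 7.6, 9.5, 17.6 and 29.7% for three arms.

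**4. If usual-care centres have no clustering** (m = 15, other arms as above): ACT versus usual care gives 5.8, 6.8, 9.2 and 13.4%; the three-arm test gives 6.3, 8.2, 13.4 and 22.6%. The centre-means test then gives 5.0 to 5.5% and 5.1 to 6.7% respectively.

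**5. Information actually available.** Power comes from the noncentral F with λ = N f² / (1 + (m − 1) × ICC). For N = 150 and m = 15, N f² = 150 × 0.0625 = 9.375.

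- Participant-level F(2,147) at ICC 0: 78%.
- Centre-means F(2,7) at ICC 0, 0.01, 0.02, 0.05, 0.10: λ = 9.38, 8.22, 7.32, 5.51, 3.91; power 58.5, 52.8, 48.0, 37.7, 27.9%.
- With 135 evaluable (13.5 per centre): 73% for the participant-level test; 53.9, 49.0, 44.9, 35.8 and 26.9% for centre means.

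The width of a two-arm interval on the pooled 7 df, relative to the participant-level interval, is √(1 + 14 × ICC) × t(0.975, 7) / t(0.975, 147). This equals 1.28, 1.35, 1.56 and 1.85 at ICC 0.01, 0.02, 0.05 and 0.10.

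**The case against.** **Data Analysis is a short summary.** It lists no error terms, its subject-level wording appears only in the T1 to T2 sentence, and an SAP may add centre. It is fair to say that the protocol omits a centre term rather than expressly excluding one. But the unit of randomisation is a design matter that the protocol itself states inconsistently, and the method it names is a participant-level one. An SAP would have to replace that test, not merely elaborate it.

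**The harm is conditional.** Two allocation sentences speak of people, and none allocates centres. This stands: the contradiction is certain, while the inflation applies only if centres are randomised. It does not rescue the text, because on the individual reading the design declaration is wrong.

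**The size rests on an assumed ICC.** This stands too. Across the range the effect runs from minor to severe, and the figures are illustrative.

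**The scenarios differ in size.** Twenty per centre means 200 people, more than the 150 planned, although 20 is the Design section's own upper figure. Thirteen per centre is 130, only near 135. Power at N = 150 is somewhat better than at 135 evaluable, so it slightly understates the cost.

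**Centre as a stratum.** No text says that randomisation is stratified by centre. Without stratification, a centre term mainly serves precision, but it costs almost nothing.

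**Conclusion.** The concern holds and must be fixed. No reading makes Design, Participants and Data Analysis agree. Under the design that the protocol declares, the analysis as written is anti-conservative for any positive ICC of change. With 15 per centre and an assumed, equal ICC of 0.01 to 0.10, the nominal 5% becomes about 7 to 21% for two arms of three centres and 7 to 29% for all three arms. It is lower if usual-care centres do not cluster, and stays at 5% if the ICC is zero. These sizes assume that centres are randomised and equal in size. If individuals are randomised, what remains is a wrong design label and an analysis without centre.

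**What to change.** State in Design whether centres or individuals are randomised, and make Participants agree.

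- **If centres:** keep the planned T0 to T1 and T1 to T2 comparisons, but analyse the change score with a linear mixed model that has a random centre effect and small-sample df, or analyse the 10 centre means (7 df for three arms). If the two time points are instead modelled as repeated measures, the model needs a random centre-by-time effect, because a centre intercept alone cancels out of the time-by-arm test. The choice of df correction can be left to the SAP.
- **If individuals within centres:** correct the design label and include centre as a stratum in the model.

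In either case, the reference to two groups in Data Analysis should be squared with the three arms.

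For individual randomisation the cost is wording and one model term. For centre randomisation it is wording, analysis work and the loss of apparent precision shown in step 5. That loss reflects how little information 10 centres carry; the correction does not create it.

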### *Intervention*

#### ACT and Exercise:

Participants with chronic pain will participate in an intervention program given twice a week for 8 weeks. ACT designed for chronic pain will be conducted by register Clinical Psychologist, and co-facilitated by registered social workers who are trained by this project and employed by the NGOs. The trained peer supporters will be matched to individual older adults to walk them through the process with regular follow-up. Exercise training program would be designed and instructed by an Exercise Specialist and trained exercise coach.

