#### Art and Exercise:

Similar to the experimental group, participants with chronic pain will participate in the sham program twice a week for 8 weeks. The Art program, conducted by an art therapist and research assistants, and will be co-facilitated by the project officers who are trained by this project and employed by the NGOs. Trained peer supporters will be matched to individual older adults to walk them through the process with regular follow-up if necessary. Exercise training program would be designed and instructed by an Exercise Specialist and trained exercise coach.

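### The participant-level mixed ANOVA has no term for session group, facilitator or centre, so if people treated together have correlated outcomes, the errors of the ACT contrasts are understated even under individual randomisation.

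*Protocol*

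**What the plan says.** **Analysis.** The Data Analysis section of the Protocol fixes the method for the main outcomes: "mixed ANOVA will be used to assess changes from T0/Intake to T1/exit between the two groups". Mixed ANOVA is named again for exit to follow-up, where the only structure mentioned is within and between subjects. No term for session group, facilitator or centre appears.

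**Delivery.** The two Intervention subsections describe parallel programmes, each held twice a week for 8 weeks. ACT is led by a clinical psychologist and "co-facilitated by registered social workers who are trained by this project and employed by the NGOs". Art is led by an art therapist with research assistants and "co-facilitated by the project officers who are trained by this project and employed by the NGOs". Both arms have an exercise specialist and coach. Peer supporters are matched to individuals. Group format, group size and numbers of facilitators are not given. Usual care is named but not described.

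**Allocation.** The Design section states: "This study adopts a cluster randomized trial design". The Participants section reads as though individuals are allocated: older adults "recruited from collaborating NGOs will be randomized into 3 different arms".

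**Sample size.** The Participants section takes an effect size of 0.25 and says that "an alpha=0.05, and power=0.8 was used to derive the total sample size of 135 participants", then "Assuming 10% attrition, total sample size = 150". No allowance for clustering is mentioned.

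**The concern.** People who attend the same sessions under the same facilitators tend to end up more alike than people who do not. That correlation arises after allocation, so randomising individuals does not remove it. A participant-level ANOVA treats each person's change as independent. It then divides by too many effective observations in the programme arms, and its standard errors come out too small.

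The two ACT contrasts are affected unequally. In ACT v art both arms would be grouped. In ACT v usual care, on the delivery described, only one would be. ACT v art is also the contrast that separates ACT from attention and exercise. At stake are confidence intervals that are too narrow and false-positive claims that are too frequent.

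**Working it through.** **1. The plan's own figures.** The attrition step reproduces exactly: 135 / (1 − 0.10) = 150. The 135 does not follow from the stated inputs alone. Reading 0.25 as Cohen's f (the metric is not stated), a one-way ANOVA of three groups at alpha 0.05 and power 0.80 needs 158, or 159 with equal arms, and 135 gives power 0.73. A between-subjects test in a 3-group, 2-time repeated-measures design gives 135 if the correlation between times is 0.7, which the Protocol does not state. No design effect is among the stated inputs.

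**2. Inputs for the check.**
- From the Protocol: 135 evaluable, three arms, nominal alpha 0.05.
- Assumed: equal allocation, so 135 / 3 = 45 per arm; individual randomisation; groups of m = 5, 9 or 15 in the ACT and art arms; no grouping in usual care; ICC of change 0.02, 0.05 or 0.10.
- The group sizes are plausible. If the Design section's 15 to 20 people are per centre and each centre ran all arms, an arm would have about 15/3 = 5 to 20/3 = 6.7 people per centre. Pooling across centres would give larger groups.

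**3. Formulae.** The design effect in a programme arm is DE = 1 + (m − 1) × ICC; in usual care it is 1. True over reported standard error is √DE for ACT v art and √((1 + DE)/2) for ACT v usual care. Type I error is approximately 2 × [1 − Φ(1.96 / ratio)].

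Worked case, m = 15 and ICC 0.05: DE = 1 + 14 × 0.05 = 1.70. For ACT v art the ratio is √1.70 = 1.30 and type I error is 13.3%. For ACT v usual care the ratio is √1.35 = 1.16 and type I error is 9.2%.

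**4. Results.**

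| m | ICC | DE | SE ratio, ACT v art | SE ratio, ACT v usual care | Type I, ACT v art | Type I, ACT v usual care |
|---|---|---|---|---|---|---|
| 5 | 0.02 | 1.08 | 1.04 | 1.02 | 5.9% | 5.5% |
| 5 | 0.05 | 1.20 | 1.10 | 1.05 | 7.4% | 6.2% |
| 5 | 0.10 | 1.40 | 1.18 | 1.10 | 9.8% | 7.4% |
| 9 | 0.02 | 1.16 | 1.08 | 1.04 | 6.9% | 5.9% |
| 9 | 0.05 | 1.40 | 1.18 | 1.10 | 9.8% | 7.4% |
| 9 | 0.10 | 1.80 | 1.34 | 1.18 | 14.4% | 9.8% |
| 15 | 0.02 | 1.28 | 1.13 | 1.07 | 8.3% | 6.6% |
| 15 | 0.05 | 1.70 | 1.30 | 1.16 | 13.3% | 9.2% |
| 15 | 0.10 | 2.40 | 1.55 | 1.30 | 20.6% | 13.3% |

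Simulation of participant-level t-tests on change scores (20,000 trials per setting) agrees: at m = 15 and ICC 0.05 and 0.10, about 13% and 21% for ACT v art, and about 9% and 13% for ACT v usual care. At ICC 0 both stay at about 5%. At ICC 0.01 with m = 15 they are 6.6% and 5.7%.

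**5. What a correct analysis costs in precision.** With three groups of 15 per arm, ACT v art has about 2 × (3 − 1) = 4 degrees of freedom. The 97.5% t quantile is then 2.78, against 1.99 on 88 degrees of freedom, a ratio of 1.40. Multiplied by SE ratios of 1.30 to 1.55 (ICC 0.05 to 0.10), intervals become about 1.8 to 2.2 times as wide as those reported.

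**The case against.** The strongest objection is that the premise is partly inferred. A reader might conclude that programme participants certainly share sessions and that usual-care participants share nothing. The documents support neither. Co-facilitation and the word programme point to groups, but no section says so, and peer support is matched to individuals. Usual care is undescribed, and its participants come from the same collaborating NGOs. This stands: the point is conditional on sessions being held in groups and on a positive ICC, and at ICC 0.01 or in small groups the inflation is minor.

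A second objection is that the Design section names a cluster randomised trial. If whole centres are allocated, people in all three arms are clustered by centre, which is the more direct defect. Session groups would then normally sit within centres, and a centre effect would do the work wherever the two coincide. This also stands. A reader might infer that a centre term never helps, or that usual care can always be modelled without clustering. Both inferences fail under the named design: a model with no centre term and no clustering in usual care would still understate the error of ACT v usual care.

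A third objection is that random effects are often left to the analysis plan. This does not remove the point, because the Protocol itself names the model and its error structure.

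**Conclusion.** The point holds in conditional form. The Protocol fixes a participant-level analysis for two programmes whose participants share facilitators and apparently sessions. Any positive correlation among people treated together makes the errors of both ACT contrasts too small, more so for ACT v art, and settling on individual randomisation would not cure it. Under the assumptions in the check (45 per arm, groups of 5 to 15, ICC 0.02 to 0.10, nothing shared in usual care), true type I error is about 6% to 21% for ACT v art and 5% to 13% for ACT v usual care. The documents do not fix where in that range the trial lies. If centres are the unit of randomisation, clustering reaches all three arms and these figures do not describe the whole problem.

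**What to change.** State the unit of randomisation, the session format, the intended group size and the number of facilitators. Record each participant's centre and session group during delivery, since these are hard to recover later.

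Replace the participant-level mixed ANOVA with a linear mixed model of change, or of the exit score adjusted for baseline, containing:
- a random session-group effect in the ACT and art arms only;
- a centre effect across all three arms, random if centres are randomised; where session group and centre coincide, the centre effect serves for both;
- Satterthwaite or Kenward-Roger degrees of freedom.

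The random effect must act on change. A group effect that is constant over time cancels from the group-by-time test and corrects nothing. Report the estimated ICC.

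If a single facilitator serves a whole arm, that person's effect is confounded with the arm and no model can separate it. It should be acknowledged as a limitation.

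The direct cost is small: the centre and session-group identifiers and a changed model statement. The cost in precision may not be. Intervals will be wider, possibly substantially if there are only about three groups per arm. The 80% power in the Participants section allows for no clustering and should be restated under an explicit group size and ICC.
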